2. OBJECTIVES AND ENDPOINTS

2.1. Objectives

Parts A and B:

The primary objective is:

- to evaluate the safety and tolerability of single and multiple oral doses of KRP-A218 in healthy subjects.

The secondary objectives are:

- to assess the PK of CCI (the active ingredient of KRP-A218) following single and multiple oral doses of KRP-A218 in healthy subjects.
- to assess the effect of food on the PK of CCI following a single oral dose of KRP-A218 in healthy male subjects.
- to assess the effect of sex on the PK of CCI following a single oral dose of KRP-A218.

The exploratory objectives are:

- to explore blood and urine samples for the metabolite profiles of CCI following single and multiple oral doses of KRP-A218 in healthy male subjects.
- to explore faecal samples for the metabolite profiles following a single oral dose of KRP-A218 in healthy male subjects.
- to explore blood and urine samples for pharmacodynamic biomarkers.
- to explore a potential effect of KRP-A218 on phospholipid-C in serum and faecal calprotectin.
- to collect blood samples for potential pharmacogenetic analyses.
- to collect continuous ECG waveforms for concentration-QTc analysis, following single oral doses of KRP-A218 in healthy subjects (Part A only).

Part C:

The primary objective is:

- to assess the effect of multiple doses of itraconazole (cytochrome P450 3A4 inhibitor) on the single-dose PK of CCI in healthy male subjects.

The secondary objectives are:

- to assess the safety and tolerability of single oral doses of KRP-A218 when co-administered with multiple oral doses of itraconazole in healthy male subjects.
- to assess the PK of itraconazole and its metabolite hydroxy-itraconazole when co-administered with KRP-A218 in healthy male subjects.

The exploratory objectives are:

- to explore blood samples for the metabolite profiles of CCI administered KRP-A218 alone and when co-administered with itraconazole in healthy male subjects.
- to explore a potential effect of KRP-A218 on phospholipid-C in serum and faecal calprotectin.
- to collect blood samples for potential pharmacogenetic analyses.

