3.1.3. Part C (Drug-Drug Interaction Study)

Part C will comprise an open-label, fixed-sequence, enrolling healthy male subjects to investigate the effect of multiple oral doses of itraconazole on the single oral dose PK of CCI in healthy subjects. There will be 1 group; Group C1, consisting of 12 male subjects. Part C will start after completion of blinded safety, tolerability, and PK data review in Part A. All subjects will receive each of the following treatments:

- Days 1 and 11: single oral dose of KRP-A218
- Day 4: 2 \times single oral doses of 200 mg itraconazole, approximately 12 hours apart
- Days 5 to 13: single oral doses of 200 mg itraconazole

The study days of dosing of itraconazole and KRP-A218 may be amended to extend the interval between the first dose of KRP-A218 and the first dose of itraconazole depending on the observed $t_{1/2}$ of CCI.

Potential subjects will be screened to assess their eligibility to enter the study within 28 days prior to the first dose administration. Subjects will be admitted into the study site on Day -1 and be confined to the study site until discharge on Day 14.

Subjects will return to the study site for a follow-up visit 7 to 10 days after the last dose of KRP-A218. The follow-up period may be extended depending on the observed $t_{1/2}$ of CCI.

[figure not shown]
Based on the ongoing review of the safety, tolerability, and PK results, additional nonresidential visits may be required. The number of additional visits per subject will not exceed 3 and will not extend beyond 28 days after each final dosing occasion. All subjects may stay in the CRU even outside treatment period due to COVID-19 risks.

The dietary state for dosing of KRP-A218 alone on Day 1 and KRP-A218 co-administered with itraconazole on Day 11 will be determined by comparing the PK data between fed and fasted state in Group A2a. Itraconazole on Days 4 to 10, 12 and 13 will be administered in the fasted state. The dose level of KRP-A218 will be confirmed based on the available safety, tolerability, and PK data in preceding Parts A and/or B of the study.

An overview of the study design is shown in [Figure 4](#), and the planned dose levels in [Figure 5](#).

[figure not shown]
A Schedule of Assessments is presented in [Appendix 6](#).

Figure 4: Study Schematic (Part C)

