7.3. Safety and Tolerability Assessments

7.3.1. Adverse Events

Adverse event definitions, assignment of severity and causality, and procedures for reporting SAEs are detailed in [Appendix 1](#).

The condition of each subject will be monitored from the time of signing the ICF to final discharge from the study. Subjects will be observed for any signs or symptoms and asked about their condition by open questioning, such as ‘how have you been feeling since you were last asked?’, at least once each day while resident at the study site and at each study visit. Subjects will also be encouraged to spontaneously report AEs occurring at any other time during the study.

Any AEs and remedial action required will be recorded in the subject’s source data. The nature, time of onset, duration, and severity will be documented, together with an Investigator’s (or designee’s) opinion of the relationship to study treatment.

Adverse events recorded during the course of the study will be followed up, where possible, until resolution or until the unresolved AEs are judged by the Investigator (or designee) to have stabilised. This will be completed at the Investigator’s (or designee’s) discretion.

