4.3. Part C (Drug-Drug Interaction Study)

Part C will comprise an open-label, fixed-sequence, enrolling healthy male subjects to investigate the effect of multiple oral doses of itraconazole on the single oral dose PK of [CCI](#) in healthy subjects. There will be 1 group; Group C1, consisting of 12 male subjects. Part C will start after completion of blinded safety, tolerability, and PK data review in Part A. All subjects will receive each of the following treatments:

- Days 1 and 11: single oral dose of KRP-A218
- Day 4: 2 \times single oral doses of 200 mg itraconazole, approximately 12 hours apart
- Days 5 to 13: single oral doses of 200 mg itraconazole

The study days of dosing of itraconazole and KRP-A218 may be amended to extend the interval between the first dose of KRP-A218 and the first dose of itraconazole depending on the observed $t_{1/2}$ of [CCI](#)

Potential subjects will be screened to assess their eligibility to enter the study within 28 days prior to the first dose administration. Subjects will be admitted into the study site on Day -1 and be confined to the study site until discharge on Day 14.

Subjects will return to the study site for a follow-up visit 7 to 10 days after the last dose of KRP-A218. The follow-up period may be extended depending on the observed $t_{1/2}$ of [CCI](#)

Based on the ongoing review of the safety, tolerability, and PK results, additional nonresidential visits may be required. The number of additional visits per subject will not

[figure not shown]
exceed 3 and will not extend beyond 28 days after each final dosing occasion. All subjects may stay in the CRU even outside treatment period due to COVID-19 risks.

The dietary state for dosing of KRP-A218 alone on Day 1 and KRP-A218 co-administered with itraconazole on Day 11 will be determined by comparing the PK data between fed and fasted state in Group A2a. Itraconazole on Days 4 to 10, 12 and 13 will be administered in the fasted state. The dose level of KRP-A218 will be confirmed based on the available safety, tolerability, and PK data in preceding Parts A and/or B of the study.

The total duration of study participation for each subject (from screening through follow-up visit) is anticipated to be up to 49 days.

[figure not shown]
An overview of the study design is shown in [Figure 4](#), and the planned dose levels in [Figure 5](#).

Figure 4: Study Schematic (Part C)

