8.7. Safety and Tolerability Assessments

8.7.1. Adverse Events

All AEs will be coded using the Medical Dictionary for Regulatory Activities (MedDRA) Version 24.0 (or higher if a new version is issued during the study; see the DMP for more details).

A treatment-emergent adverse event (TEAE) will be defined as an AE that starts during or after the first dose, or starts prior to the first dose and increases in severity after the first dose.

A treatment-related TEAE will be defined as a TEAE with a relationship of possibly related or related to the study treatment, as determined by the investigator.

For Group A2a in Part A, the assignment of TEAEs to treatments will be as follows:

- A TEAE that starts or increases in severity during or after Period 1, Day 1 dosing and prior to Period 2, Day 1 dosing will be assigned to '3 mg KRP-A218 (Fasted Male)'.
- A TEAE that starts or increases in severity during or after Period 2, Day 1 dosing will be assigned to '3 mg KRP-A218 (Fed Male)'.

For Part C, the assignment of TEAEs to treatments will be as follows:

- A TEAE that starts or increases in severity during or after Day 1 dosing and prior to Day 4 dosing will be assigned to 'XX mg KRP-A218 Alone'.
- A TEAE that starts or increases in severity during or after Day 4 dosing and prior to Day 11 dosing will be assigned to '200 mg Itraconazole Alone'.
- A TEAE that starts or increases in severity during or after Day 11 dosing will be assigned to 'XX mg KRP A218 + 200 mg Itraconazole'.

All AEs will be listed. In addition to the data recorded in the database, the listings will include derived onset time and duration. Onset time will be calculated from the time of the last associated dose for TEAEs only. Where the last associated dose is referring to the last dose received prior to the start of a TEAE.

The frequency of subjects with TEAEs and the number of TEAEs will be summarised for the following categories:

- TEAEs (overall, serious, leading to discontinuation, and leading to death) by treatment
- TEAEs by severity and treatment
- Treatment-related TEAEs (overall, serious, leading to discontinuation, and leading to death) by treatment
- Treatment-related TEAEs by severity and treatment

The frequency of subjects will be summarised separately for TEAEs and treatment-related TEAEs by the following:

- System organ class, preferred term, and treatment
- Preferred term and treatment

For the AE data the following rules will apply:

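### Part C assigns adverse events to KRP-A218 alone for a nominal 3 days but to KRP-A218 plus itraconazole for a nominal 7 to 10 days, with no adjustment for observation time

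*SAP*

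**What the plan says.** SAP 4.3 gives the Part C dosing as "Days 1 and 11: single oral dose of KRP-A218", a double itraconazole dose on Day 4, and "Days 5 to 13: single oral doses of 200 mg itraconazole". Twelve men receive the whole sequence, open-label.

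SAP 8.7.1 divides the TEAEs among three columns:

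- For the KRP-A218 Alone column, the rule is: "A TEAE that starts or increases in severity during or after Day 1 dosing and prior to Day 4 dosing will be assigned to".
- For the Itraconazole Alone column, the rule is: "A TEAE that starts or increases in severity during or after Day 4 dosing and prior to Day 11 dosing will be assigned to".
- For the KRP-A218 + Itraconazole column, the rule is: "A TEAE that starts or increases in severity during or after Day 11 dosing will be assigned to". No end point is given.

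The end of the third window has to be taken from the protocol. Section 7.3.1 states: "The condition of each subject will be monitored from the time of signing the ICF to final discharge from the study". Section 3.1.3 states: "Subjects will return to the study site for a follow-up visit 7 to 10 days after the last dose of KRP-A218". That section also allows both the gap before the first itraconazole dose and the follow-up period to be extended, depending on the observed half-life.

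SAP 8.7.1 then tabulates subjects with TEAEs and numbers of TEAEs by treatment, overall and for treatment-related events. Neither document plans a common window or a rate per subject-day, or warns about unequal observation time.

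**The concern.** One of the secondary objectives of Part C is "to assess the safety and tolerability of single oral doses of KRP-A218 when co-administered with multiple oral doses of itraconazole". A reader of the by-treatment AE table will naturally compare the KRP-A218 Alone column with the combination column, because the same 12 men contribute to both.

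The two columns do not cover the same length of time. The combination column also includes the itraconazole doses on Days 12 and 13 and roughly 4 to 7 days at home after discharge on Day 14. Any event that KRP-A218 causes after Day 4 dosing is counted under Itraconazole Alone, which lowers the KRP-A218 Alone count further. Background events such as the headache, cold symptoms and sore throat already reported in Part A (Protocol 1.3) have more time to appear in the combination column. A difference in the table could therefore be read as an interaction effect when it only reflects longer collection.

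**Working it through.** **1. Reproduce the plan's figure.** Protocol 3.1.3 and SAP 4.3 give a maximum participation of 49 days. With 28 screening days, the last KRP-A218 dose on Day 11 and at most 10 days to follow-up: 28 + 11 + 10 = 49. The latest nominal visit is therefore Day 21 and the earliest is Day 11 + 7 = Day 18.

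**2. Window lengths (nominal).**
- KRP-A218 Alone: Day 4 − Day 1 = 3 days.
- Itraconazole Alone: Day 11 − Day 4 = 7 days.
- KRP-A218 + Itraconazole: Day 18 to 21 − Day 11 = 7 to 10 days.
- Combination to alone: 7/3 = 2.3 to 10/3 = 3.3.

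**3. Expected counts if itraconazole adds nothing.** The documents give no background AE rate, so a range is assumed. With a constant hazard h per day, P(at least one TEAE in d days) = 1 − exp(−h·d), and the expected number of subjects is 12·P. If p is the proportion with an event in 3 days, h = −ln(1 − p)/3.

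For p = 10%: P(7) = 1 − 0.9^(7/3) = 21.8% and P(10) = 1 − 0.9^(10/3) = 29.6%. For p = 20%: 40.6% and 52.5%.

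The last column is the probability that strictly more subjects have a TEAE in the combination window. It comes from two binomials with n = 12, treated as independent. This is an approximation, since the subjects are the same.

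| Assumed background | Alone, 3 days | Combination, 7 to 10 days | Ratio | P(strictly more) |
|---|---|---|---|---|
| 10% per 3 days | 1.2 | 2.6 to 3.6 | 2.2 to 3.0 | not computed |
| 20% per 3 days | 2.4 | 4.9 to 6.3 | 2.0 to 2.6 | not computed |
| 1% per day | 0.35 | 0.81 to 1.14 | 2.3 to 3.2 | 0.45 to 0.57 |
| 2% per day | 0.70 | 1.57 to 2.18 | 2.2 to 3.1 | 0.59 to 0.73 |
| 5% per day | 1.67 | 3.54 to 4.72 | 2.1 to 2.8 | 0.76 to 0.89 |
| 10% per day | 3.11 | 6.04 to 7.59 | 1.9 to 2.4 | 0.85 to 0.96 |

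**4. Opposite limiting case: events follow drug level only, with no background and an unchanged half-life.** Protocol 1.3 reports a half-life of about 15 to 18 h. The share of a simple exponential decay left after 72 h is 2^(−72/t½), about 3% to 6% over the group means of 14.8 to 18.2 h. With 95% of a total drug-driven hazard of 0.2 (assumed) falling in the first 72 h, expected counts are 12·(1 − exp(−0.19)) = 2.08 against 12·(1 − exp(−0.20)) = 2.18, a ratio of 1.05. Adding a 2% per day background to that hazard gives 2.65 against 3.46 to 3.96, a ratio of 1.3 to 1.5.

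**5. After matching.** With 72 h after each KRP-A218 dose and the same hazard, expected counts are equal (0.70 and 0.70 at 2% per day; 1.67 and 1.67 at 5% per day). P(strictly more) falls to 0.22 to 0.41 across the four daily rates.

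**The case against.** The strongest reply is that this is a descriptive table and the information is not lost. Several parts of that stand.

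- **Other evidence.** A reader might infer that the AE columns are the only safety evidence in Part C. They are not. SAP 3.2 also names body weight, laboratory tests, ECG, vital signs, Bristol Stool Chart, faecal occult blood and physical examination. SAP 8.7.2 to 8.7.5 summarise laboratory, vital-sign, ECG, stool and occult-blood data by timepoint, and window length does not affect those summaries.
- **Recoverability.** A reader might infer that a true increase could not be told from longer collection. The listings carry the recorded data, so a matched count can be made by hand for 12 subjects. The derived onset time does not do this by itself, because it restarts at each later dose, including itraconazole on Days 12 and 13.
- **Partial comparator.** The Itraconazole Alone column spans 7 days in the same men and would also collect background events.
- **Part A.** The longer windows in Part A might suggest an inconsistency in the SAP. They do not show one: itraconazole starts on Day 4 in Part C, so later events cannot be assigned cleanly to KRP-A218 alone.
- **Ascertainment.** Protocol 7.3.1 requires at least daily questioning only while subjects are resident. Events at home may be under-collected, which would reduce the excess.
- **Late events matter.** Protocol 3.4 expects itraconazole to inhibit metabolism if CYP3A4 is the main route. Assume purely metabolic elimination and full loss of the lowest CYP3A share in Protocol 1.2 (68.4%). The half-life then becomes 15/0.316 to 18/0.316, about 47 to 57 h, and some 35% to 42% of drug remains at 72 h. A 72 h comparison used alone could miss real interaction events.

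What does not fall away is that the planned by-treatment counts have unequal windows and nothing beside them says so. The treatment-related tables help only in part, since causality is judged by the investigator in an open-label part. The general caution in SAP 8.1 concerns the unpowered sample size, not observation time.

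**Conclusion.** The point holds as a presentation weakness with a cheap remedy. The nominal windows differ by a factor of 2.3 to 3.3, and the by-treatment counts ignore this. Under a constant background rate and no itraconazole effect, the combination column is expected to show about 2 to 3 times as many subjects with a TEAE. That size rests on assumed rates and a constant hazard. It shrinks to about 1.05 if events only follow drug level and clearance is unchanged.

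It would be tempting to say that the table will show more events with co-administration. The documents do not support that: they give no background rate, the windows are nominal and may be extended, and 12 subjects leave room for chance. At 2% per day, for example, a tie has probability 0.17 to 0.25 and a reversal 0.09 to 0.16. No test is invalidated, because SAP 8.7.7 plans no inference on safety.

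**What to change.** Keep the full-window TEAE summaries and the listings as planned. Add to SAP 8.7.1 one supplementary Part C table with three columns:

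- TEAEs starting 0 to 72 h after the Day 1 KRP-A218 dose;
- TEAEs starting 0 to 72 h after the Day 11 KRP-A218 dose;
- TEAEs starting more than 72 h after the Day 11 dose, placed next to the second column so that late events from slowed clearance stay visible.

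State the window length in each column header, in this table and in the full-window tables. Subjects are resident from Day −1 to Day 14, so both 72 h windows are in-house with the same daily questioning.

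The cost is SAP wording and one extra table, with no change to the protocol, sampling or conduct. The matched columns do not capture late-onset events, so they must be read together with the full-window table and must not replace it. Matching also does not remove period effects of the fixed sequence.

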^k To be recorded after the subject has been supine and at rest for at least 5 minutes.

^l Full physical examination.

^m Symptom-directed physical examination.

ⁿ Prior to discharge.

^o To be performed at approximately the same time as on Day 1.

^p Subjects will receive the IMP at the same time as Day 1 in Treatment Period 1 and 30 minutes after starting a high-fat breakfast.

^q If the latest result during the treatment period is positive, faecal samples will be collected for faecal occult blood test at the follow-up visit (within -2 day), as far as possible.

^r The interval between dosing is up to and including Day -1 of Treatment Period 2. The washout and follow-up periods may be extended depending on the observed $t_{1/2}$ of CCI

Table 11: Schedule of Assessments-Part B (Multiple-Dose) [Screening to Day 1]

Day	Screening	Treatment Period													
		-28 to -2	-1	Pre	0	0.25	0.5	0.75	1	1.5	2	3	4	6	8
Time Postdose(h)															
Informed consent	X														
Inclusion/exclusion criteria	X	X													
Demographic data	X														
Medical history	X	X ^a													
Urinary drug and cotinine screen	X	X													
Alcohol breath test	X	X													
Scrology	X														
Height	X														
IMP administration															
KRP-A218 or placebo ^b				X ^c											
Pharmacokinetics															
Blood sampling for the PK of CCI			X		X	X	X	X	X	X	X	X	X	X	X
Exploratory analyses															
Blood sampling for metabolite profiling ^d			X												
Urine collection for metabolite profiling ^{d,e}			<----X---->												
Pharmacogenetics			X												
Safety and tolerability															
Adverse event recording			<----->												
Prior/concomitant medication monitoring			<----->												
Body weight	X	X													
Haematology, clinical chemistry, coagulation, and urinalysis ^f	X	X													
Faecal occult blood test ^g	X	<----X---->		<-----X----->											
Bristol Stool Chart ^h		<----X---->		<-----X----->											
Blood pressure and pulse rate, and respiratory rate ⁱ	X	X	X ^j					X				X		X	X
Oral body temperature	X	X	X												
12-lead ECG for safety assessment ^k	X	X	X ^j					X				X		X	X
Physical examination			X ^l												
Abdominal examination			X								X				

Table 11: Schedule of Assessments-Part B (Multiple-Dose) [Day 2 to Day 13]

Day	Treatment Period											
	2	3	4	5	6	7	8	9	10	11	12	13
Time Postdose(h)	24	48	72	96	120	144	168	192	216	240	264	288
IMP administration												

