^a Interim medical history.^b Subjects will receive the IMP once daily at the same time as Day 1 in the fasted state (at least 10 hours).^c Subjects will be fasted until 4 hours after dosing, after which time a meal will be provided.^d Collected in Group B1 only.^e Spot urine sample will be collected any time prior to dosing. 24-hour urine samples will be collected on 0 to 24 hours postdose on Day 14.^f Subjects will be fasted at least 6 hours before collection.

^g Faecal occult blood test will be performed once each during the following sampling periods: Screening, Day -1 to prior to dosing, 0 to 24, 24 to 96, 96 to 168, 168 to 240 hours postdose on Day 1, 240 hours postdose on Day 1 to 0 hours on Day 14, and 0 to 72 hours postdose on Day 14. On screening, faecal samples will be collected to confirm eligibility for enrollment. For the other sampling periods, faecal samples will be collected as far as possible.

^h To be assessed when collecting faecal samples for faecal occult blood test in the treatment period.

ⁱ Subjects should be supine for at least 5 minutes before blood pressure and pulse rate measurements.

^j To be measured in triplicate at approximately 2-minute intervals.

^k To be recorded after the subject has been supine and at rest for at least 5 minutes.

^l Full physical examination.

^m Symptom-directed physical examination.

ⁿ Immediately before dosing.

^o From waking-up to before dosing.

^p To be performed at approximately the same time as on Day 1.

^q From waking-up to before breakfast.

^r If the latest result during the treatment period is positive, faecal samples will be collected for faecal occult blood test at the follow-up visit (within -2 day), as far as possible.

^s Prior to discharge.

^t The follow-up period may be extended depending on the observed $t_{1/2}$ of **CCI**

Table 12: Schedule of Assessments-Part C (DDI) [Screening to Day4]

Day	Screening	Treatment Period 1																
		-28 to -2	-1	1	2	3	4	6	8	12	24	36	48	72				
Time Postdose (h)		Pre	0	0.25	0.5	0.75	1	1.5	2	3	4	6	8	12	24	36	48	72
Informed consent	X																	
Inclusion/exclusion criteria	X	X																
Demographic data	X																	
Medical history	X	X ^a																
Urinary drug and cotinine screen	X	X																
Alcohol breath test	X	X																
Serology	X																	
Height	X																	
KRP-A218 and itraconazole administration^r																		
KRP-A218			X ^b															

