In each of Groups A1 to A5, 6 subjects will receive KRP-A218 and 2 subjects will receive placebo in accordance with a randomisation schedule. In Groups A1, A2b, and A3 to A5, all doses will be administered in the fasted state on the morning of Day 1. For Group A2a, Period 1, Day 1 doses will be administered in the fasted state and Period 2, Day 1 doses will be given 30 minutes after starting a standard high-fat breakfast. Each subject in Groups A1, A2b, and A3 to A5 will receive only a single dose of KRP-A218 or placebo during the study. In Group A2a, subjects will have the same treatment in both periods, such that each subject will receive 2 single doses of KRP-A218 or placebo during the study.

All groups in Part A (with the exception of Group A2a in Treatment Period 2) will receive the study treatment using a sentinel approach.

The total duration of study participation for each subject (from screening through follow-up visit) is anticipated to be up to 39 days (Groups A1, Group A2b [female subjects only], A3 to A5) or up to 50 days (Group A2a; male subjects only).

[figure not shown]
An overview of the study design is shown in [Figure 1](#) and [Figure 2](#), and the planned dose levels in [Figure 5](#).

Figure 1: Study Schematic (Part A; Groups A1, A2b [Female subjects Only], and A3 to A5)

*CRU = Clinical Research Unit

The follow-up period may be extended depending on the observed $t_{1/2}$ of CCI [REDACTED]

Figure 2: Study Schematic (Part A; Group A2a [Male subjects Only])

The washout and follow-up periods may be extended depending on the observed $t_{1/2}$ of CCI

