8.1.5. Definitions of Baseline and Change from Baseline

The baseline will be defined as the last value recorded prior to the first dose. If the date/time of the value is incomplete or missing, it will be excluded from the baseline calculation, unless the incomplete date/time indicates the value was recorded prior to the first dose.

Individual changes from baseline will be calculated by subtracting the individual subject’s baseline value from the value at the postdose timepoint.

The summary statistics for change from baseline will be derived from individual subjects’ values (eg, mean change from baseline will be the mean of the individual changes from baseline for all subjects, rather than difference between the mean value at the postdose timepoint and mean value at baseline).

See [Section 8.1.4](#) for more detail on handling repeat and unscheduled readings in the calculations. See [Section 8.1.3](#) for more detail on handling of triplicate readings in the calculations.

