- For the derivation of treatment-emergent status (applicable to all AEs): If the start date/time of an AE is incomplete or missing, an AE will be assumed to not be a TEAE, unless the incomplete start date/time or the end date/time indicates an AE started after the first dose.

- For the derivation of treatment-related status (applicable to TEAEs only): If the study treatment relationship for a TEAE is missing, a TEAE will be assumed to not be a treatment-related TEAE.
- For the derivation of onset time (applicable to TEAEs only): If the start date/time of a TEAE is missing, onset time will not be calculated. If the start date/time of a TEAE is incomplete, where possible, the minimum possible onset time will be calculated and presented in ' \geq DD:HH:MM' format (eg, if the date/time of the last associated dose is 01MAY2019/08:00 and recorded start date/time of a TEAE is 03MAY2019, then the minimum possible onset time will be calculated by assuming a TEAE started at the first hour and minute of 03MAY2019 [03MAY2019/00:00], thus will be presented as onset time \geq 01:16:00 in the listing). If the start date of a TEAE is the same as the date of the last associated dose but the start time of a TEAE is missing, an onset time will be presented as ' \geq 00:00:01'. Any clock changes will be accounted for in the derivation.
- For the derivation of duration (applicable to all AEs): If the end date/time of an AE is missing, duration will not be calculated. If the start or end date/time of an AE is incomplete, where possible, the maximum possible duration will be calculated and presented in ' \leq DD:HH:MM' format (eg, if the start of an AE date/time is 01MAY2019/08:00 and its recorded end date/time is 03MAY2019, then the maximum possible duration will be calculated by assuming an AE ended at the last hour and minute of 03MAY2019 [03MAY2019/23:59], thus will be presented as duration \leq 02:15:59 in the listing). Any clock changes will be accounted for in the derivation.
- For the calculation of TEAE summary statistics: If the severity of a TEAE is missing, that TEAE will be counted under the 'missing' category.
- For the calculation of TEAE summary statistics: If a subject experienced multiple TEAEs with the same preferred term for the same treatment, this will be counted as 1 TEAE for that treatment under the maximum severity recorded.

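### Minor: in SAP 8.7.1 an untimed AE on the first-dose day defaults to not treatment-emergent, and the number of TEAEs counts subject-by-term pairs, not events

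*SAP*

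**What the plan says.** **Treatment-emergent status.** SAP 8.7.1 defines a TEAE as an AE that begins at or after the first dose, or that begins earlier and worsens after it. Where the start is incomplete or missing, the AE is "assumed to not be a TEAE, unless the incomplete start date/time or the end date/time indicates an AE started after the first dose".

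**Onset time.** A later bullet in the same list opens "For the derivation of onset time (applicable to TEAEs only". For an event dated on the day of its last associated dose, it adds that if "the start time of a TEAE is missing, an onset time will be presented as" at least 00:00:01.

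**Counting.** The same section promises two statistics for the overview and severity categories: how many subjects had TEAEs, and how many TEAEs there were. The last rule in the list then counts several TEAEs of one preferred term, in one subject on one treatment, as a single TEAE at the highest recorded severity. The system organ class and preferred term tables give subject frequencies only. All AEs are listed.

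**The concern.** Safety and tolerability is the primary objective of Parts A and B. SAP 8.7.7 plans no inferential safety analysis, so the TEAE tables are the main AE summary, with 6 or 8 active subjects per column.

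1. An AE dated on the first-dose day with no clock time may have started before or after the dose. The SAP resolves that doubt towards not treatment-emergent, although most of the day follows a morning dose. Any such event leaves every TEAE table, and its subject may leave the incidence.
2. A reader who sees a number of TEAEs beside a number of subjects will take the first as an event count. It is not one. Over the 14 dosing days of Part B, a complaint that recurs on several days shows as one, so the overview cannot separate a single episode from a recurring one. This acts on complete data.

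**Working it through.** **Step 1. The SAP's own partial-date example.** Dose 01MAY2019/08:00, event dated 03MAY2019.
- Minimum onset: 03MAY2019/00:00 minus 01MAY2019/08:00 = 01:16:00.
- Maximum duration, for an AE that starts at 01MAY2019/08:00 and ends on 03MAY2019: 03MAY2019/23:59 minus 01MAY2019/08:00 = 02:15:59.

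Both match the SAP, which therefore treats an untimed date as the interval 00:00 to 23:59.

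**Step 2. The same interval applied to TEAE status.** Assume a first dose at 08:00 and no recorded worsening.

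| Recorded start, no clock time | Possible onset | SAP rule | Reversed default |
|---|---|---|---|
| Day before first dose | all predose | not a TEAE | not a TEAE |
| First-dose day | 00:00 to 23:59, both sides of the dose | not a TEAE | TEAE |
| First-dose day, ended 07:00 that day | 00:00 to 07:00, all predose | not a TEAE | not a TEAE |
| Day after first dose | all postdose | TEAE | TEAE |

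The end date/time gives only onset ≤ end. An end before the dose proves predose onset. An end after the dose leaves the interval on both sides of the dose. So the end can never supply the evidence that the exception asks for. In the single-dose groups, the same-day onset-time provision is left with almost nothing to act on; it can still operate for later doses in Group A2a and in Parts B and C.

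**Step 3. Are first doses given in the morning?**
- Groups A1, A2b and A3 to A5: stated in SAP 4.1, "all doses will be administered in the fasted state on the morning of Day 1".
- Group A2a: inferred from Protocol Appendix 6, Table 10, footnote p, "Subjects will receive the IMP at the same time as Day 1 in Treatment Period 1 and 30 minutes after starting a high-fat breakfast".
- Part B: inferred. Table 11, footnote b, has "Subjects will receive the IMP once daily at the same time as Day 1 in the fasted state", and SAP 4.2 makes the Day 14 dose a morning dose. Day 1 is then also a morning dose under the planned once-daily regimen.

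**Step 4. Postdose share of the first-dose day.** Share = r × post / (r × post + pre), where r is the ratio of postdose to predose AE rate. The documents give neither clock times nor r; both are assumed.

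| Dose time | r = 1 | r = 2 |
|---|---|---|
| 07:00 | 17/24 = 70.8% | 34/41 = 82.9% |
| 08:00 | 16/24 = 66.7% | 32/40 = 80.0% |
| 11:00 | 13/24 = 54.2% | 26/37 = 70.3% |

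**Step 5. Size of one reclassified subject with no other TEAE.**
- Part A active column: 1/6 = 16.7 points.
- Part B active column: 1/8 = 12.5 points.
- Pooled Part A placebo: 6 groups × 2 = 12; 1/12 = 8.3 points.

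If the subject has another TEAE, overall incidence does not move. If 1% to 20% of first-day TEAEs lacked a time (assumption), 0.01 × 20 = 0.2 to 0.20 × 20 = 4 of every 20 would be lost.

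**Step 6. The counting rule.** With k recorded episodes of one term in one subject and treatment, the share not counted is (k − 1)/k: 50% at k = 2 and 67% at k = 3.

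Illustration on one treatment: term X in 3 subjects (2, 1 and 1 episodes) and term Y in 2 subjects (3 and 1 episodes).
- Events: 2 + 1 + 1 + 3 + 1 = 8.
- SAP count: 3 + 2 = 5, which is 1 − 5/8 = 37.5% fewer.
- Sum of the preferred-term subject counts: 3 + 2 = 5, the same figure.

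**The case against.** **On status.** The exception names the end date/time, and a literal reading leaves that limb empty. One could argue that the author meant a postdose end to make an untimed AE a TEAE; most of the loss would then disappear. That may be the intent, but the text asks for an indication that the AE started after the dose, and an end time cannot give one. If the intent differs from the text, the text still needs changing.

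The argument on rarity stands. Protocol 7.3.1 has time of onset documented and subjects questioned at least daily, and they are resident from Day -1. The first-dose day is among the days least likely to lack an onset time. The rule also applies equally to placebo.

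The baseline rule in SAP 8.1.5 is no proof of inconsistency. A value with an incomplete time is handled so that "it will be excluded from the baseline calculation, unless the incomplete date/time indicates the value was recorded prior to the first dose". Both rules ask for positive evidence before a record enters the category. The comparison shows only that the SAP does not presume untimed records to be predose everywhere.

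**On counting.** The rule is stated openly, so it is a disclosed convention, and the listings carry onset time and duration for each event. The TFL shells are a separate document that I have not seen; a label or footnote there may already state the unit. The documents do not say how severity changes within one episode are recorded, so a true event count needs an additional rule. All of this stands, and it makes the point one of labelling and definition.

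**Conclusion.** Both points hold on the text of SAP 8.7.1, as minor improvements.

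1. An untimed AE on the first-dose day is classed as not a TEAE, and with morning dosing that is the less likely answer: 54% to 83% of the probability lies postdose under the assumptions in Step 4. The default can understate incidence by the one-subject steps in Step 5. How often it would do so is unknown, and probably rarely.
2. The number of TEAEs is a subject-by-preferred-term count.

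Four stronger readings are tempting and not supported:
- *The TEAE tables are understated.* They can be; no rate of missing times or of recurrence is given.
- *The onset-time bullet contradicts the status bullet.* It is limited to events already classed as TEAEs.
- *Dose escalation is put at risk.* Protocol 3.6 and 3.7 rest on review of the accumulating data and on the events themselves, not on these tables.
- *The number of TEAEs is redundant throughout.* Only its overall row equals the sum of preferred-term subject counts; the severity, serious, discontinuation and death rows cannot be recovered that way.

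AEs with a wholly missing start date are a separate convention and are not challenged here.

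**What to change.** In SAP 8.7.1, before unblinding:

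1. Class an AE dated on the first-dose day with no clock time as a TEAE unless other recorded data show that it started before dosing and did not worsen afterwards. Footnote each such event. Its date already places it under the first treatment.
2. Apply the one-per-term, maximum-severity rule to subject counts only. In the number of TEAEs, count each recorded episode, with severity changes inside one episode counted once. Otherwise, relabel the statistic as a subject-by-preferred-term count.

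**Cost.** A few sentences, matching TFL footnotes and no new data. Counting episodes also needs a short rule for linking severity records to an episode; relabelling does not. Under (1), a few truly predose events may be attributed to treatment or placebo. Under (2), one subject with many recurrences can dominate the event count, so the subject count must stay beside it.
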